### 6.3. Lifestyle and/or Dietary Requirements

Throughout the study, subjects may undergo medical assessments and review of compliance with requirements before continuing in the study.

## 6.3.1. Meals and Dietary Restrictions

Subjects will be required to fast overnight (at least 8 hours) prior to study drug administration on Day 1. Fluids will be restricted from 1 hour prior to and until 1 hour after oral dosing, with the exception of water required for study drug administration. Otherwise, water will be freely available at all times. A standard meal will be given to the subjects no sooner than 4 hours after the oral dose. Meals will be provided as appropriate at all other times.

Subjects will refrain from consuming grapefruits or grapefruit-containing products, Seville oranges or Seville orange-containing products, star fruits or star fruit-containing products, pomelo, poppy seeds, or commercial apple juice or orange juice within 7 days prior to dosing until the final PK sample is collected. If this situation arises, inclusion or ongoing participation of the subject may be at the discretion of the investigator, in consultation with the sponsor or designee.

## 6.3.2. Caffeine, Alcohol, and Tobacco

Subjects will refrain from consuming caffeine- or xanthine-containing food and drinks within 24 hours prior to Check-in until discharge from the CRU.

Alcohol will not be permitted from 48 hours prior to Check-in until discharge from the CRU.

Smoking will not be permitted throughout the study. Subjects will not have used any tobacco- or nicotine-containing products (including, but not limited to, cigarettes, pipes, cigars, chewing tobacco, nicotine patches, nicotine lozenges, or nicotine gum) within 3 months prior to Check-in and during the entire study.

## 6.3.3. Activity

No strenuous physical activity will be allowed for 72 hours prior to dosing and during the study.

#### 6.4. Screen Failures

Individuals who do not meet the criteria for participation in this study (screen failure) may not be re-screened.

#### 7. Treatment

#### 7.1. Treatment Administered

This study involves a comparison of a single 50-mg oral dose of LY3314814 administered concurrently with an IV formulation containing approximately 100  $\mu$ g [ $^{13}$ C4 $^{15}$ N3]-LY3314814 infused over 2 hours. Table AZEP.2 shows the treatment administered.

On Day 1, 1 tablet of LY3314814 will be administered orally with approximately 240 mL of room temperature water in the morning in a sitting position.

On Day 1, approximately 100  $\mu$ g [ $^{13}$ C4 $^{15}$ N3]-LY3314814 will be administered as an IV infusion over 2 hours at an approximate rate of 15 mL/hour, in the semi-recumbent position. The IV infusion will be initiated at approximately the same time as the oral dose is administered.

Table AZEP.2. Treatments Administered

Treatment Name	LY3314814	$[^{13}C_4^{15}N_3]$ -LY3314814a
Dosage Formulation	50-mg tablets	Solution
Dosage Level	50 mg	100 μg
Route of Administration	Oral	Intravenous infusion
Dosing Instructions	1 tablet taken on Day 1	2-hour infusion

a Dosage information and administration instructions for [\frac{13}{6}C\_4\frac{15}{6}N\_3]-LY3314814 will be provided in a separate pharmacy manual.

The investigator or designee is responsible for:

- explaining the correct use of the investigational product(s) to the site personnel,
- verifying that instructions are followed properly,
- maintaining accurate records of investigational product dispensing and collection,
- and returning all unused medication to Lilly or its designee at the end of the study.

**Note:** In some cases, sites may destroy the material if, during the investigative site selection, the evaluator has verified and documented that the site has appropriate facilities and written procedures to dispose of clinical trial materials.

## 7.1.1. Packaging and Labeling

Each LY3314814 tablet is oval, biconvex, plain, dark tan, and film-coated. Tablets contain 50 mg LY3314814 and excipients and will be provided in high-density polyethylene bottles.

Information regarding the  $[^{13}C_4^{15}N_3]$ -LY3314814 solution for IV infusion will be provided in a separate pharmacy manual.

Clinical trial materials will be labeled according to the country's regulatory requirements.

#### 7.1.2. Retention Samples

Samples of LY3314814 will be retained and stored according to the storage conditions listed on the product label by the site (or facility approved by Lilly) for at least 5 years following the date on which the last application or supplemental application to the Food and Drug Administration (FDA) is approved, or, if such application or supplemental application is not approved, at least 5 years following the date of completion of the study.

## 7.2. Method of Treatment Assignment

All subjects will receive the same treatment; this study will not be subject to randomization.

## 7.2.1. Selection and Timing of Doses

Doses will be administered on the morning of Day 1, preceded by an overnight fast of at least 8 hours and followed by a fast of at least 4 hours post-oral-dose. See Section 6.3.1 for meal and dietary restrictions.

The actual time of all dose administrations will be recorded in the subject's electronic case report form (eCRF).

## 7.3. Blinding

This is an open-label study.

#### 7.4. Dose Modification

Dose adjustments are not allowed for this study.

## 7.4.1. Special Treatment Considerations

#### 7.4.1.1. Premedication for Infusions

Premedication for the infusion is not planned. However, if an infusion reaction occurs, appropriate medication may be used as determined by the study investigator.

#### 7.4.1.2. Management of Infusion Reactions

The risk of an infusion reaction is anticipated to be small; however, because this is the first administration of IV [ $^{13}C_4^{15}N_3$ ]-LY3314814, all subjects should be monitored closely. Symptoms and signs that may occur as part of an infusion reaction include, but are not limited to, fever, chills, nausea, headache, bronchospasm, hypotension, angioedema, throat irritation, rash, pruritus, myalgia, and dizziness. In the event that a significant infusion reaction occurs, the following guidance should be followed:

- the investigational product infusion should be slowed or stopped, depending on the symptoms/signs present
  - o if slowed, the infusion should be completed at the slower rate, as tolerated
  - o if stopped, no further attempts to administer the investigational product will be made

o supportive care should be employed in accordance with the symptoms/signs

## 7.4.1.3. Safety Protocol in the Event of a Retrospective Positive Sterility Finding from Extemporaneously Prepared Study Treatment

If a positive sterility finding arises in the terminally sterile filtered product, the subjects who were dosed from the impacted batch should be immediately contacted and asked to return to the CRU for a full medical examination. This should include a physical examination/medical assessment, including blood pressure, pulse rate, and body temperature. Blood samples should be collected for culture and assayed for inflammatory markers such as C-reactive protein and elevations in white blood cell counts. If the signs and symptoms indicate a subject is suffering from possible infection(s), they will be clinically managed, treated, and followed up until resolution. Any AEs will be recorded as appropriate.

#### 7.5. Preparation/Handling/Storage/Accountability

Only participants enrolled in the study may receive investigational product and only authorized site staff may supply or administer study treatment. All study treatments should be stored in an environmentally controlled and monitored (manual or automated) area in accordance with the labeled storage conditions with access limited to the investigator and authorized site staff.

The investigator, institution, or the head of the medical institution (where applicable) is responsible for study treatment accountability, reconciliation, and record maintenance (such as receipt, reconciliation, and final disposition records).

The [ $^{13}C_4^{15}N_3$ ]-LY3314814 solution for IV infusion will be prepared at the study site. Details of the preparation and storage of the IV solution will be provided in separate instructions to the site.

## 7.6. Treatment Compliance

The investigational product will be administered at the clinical site, and documentation of treatment administration will occur at the site.

## 7.7. Concomitant Therapy

Drugs or substances that are known strong inducers or inhibitors of CYP3A, strong inhibitors or inducers of Pgp, or inhibitors of BCRP are specifically excluded within 14 days prior to the administration of study drug and during the study. Additional drugs are to be avoided during the study unless required to treat an AE or for the treatment of an ongoing medical problem.

If the need for concomitant medication arises, inclusion or continuation of the subject may be at the discretion of the investigator after consultation with a Lilly clinical pharmacologist (CP) or clinical research physician (CRP). Occasional acetaminophen (paracetamol) up to a 2-gram dose in a 24-hour period may be used at the discretion of the investigator. Any additional medication used during the course of the study must be documented.

## 7.8. Treatment after the End of the Study

Not applicable for this study.

#### 8. Discontinuation Criteria

#### 8.1. Discontinuation from Study Treatment

Subjects who discontinue the investigational product early will have procedures performed as shown in the Schedule of Activities (Section 2).

## 8.1.1. Discontinuation of Inadvertently Enrolled Subjects

If the investigator identifies a subject who did not meet enrollment criteria and was inadvertently enrolled prior to any dosing, the subject will be discontinued from the study with no further data collection or study procedures performed. If the investigator identifies a subject who did not meet enrollment criteria and was inadvertently enrolled and dosed, the subject will be discontinued from the study and early discontinuation procedures performed.

## 8.2. Discontinuation from the Study

Subjects will be discontinued in the following circumstances:

- enrollment in any other clinical trial involving an investigational product or enrollment in any other type of medical research judged not to be scientifically or medically compatible with this study
- participation in the study needs to be stopped for medical, safety, regulatory, or other reasons consistent with applicable laws, regulations, and good clinical practice (GCP)
- investigator decision
  - o the investigator decides that the subject should be discontinued from the study
- subject decision
  - o the subject, requests to be withdrawn from the study

Subjects who discontinue the study early will have early discontinuation procedures performed as shown in the Schedule of Activities (Section 2).

## 8.3. Subjects Lost to Follow-up

A subject will be considered lost to follow-up if he or she repeatedly fails to return for scheduled visits and is unable to be contacted by the study site. Site personnel are expected to make diligent attempts to contact subjects who fail to return for a scheduled visit or were otherwise unable to be followed up by the site.

## 9. Study Assessments and Procedures

Section 2 lists the Schedule of Activities, detailing the study procedures and their timing (including tolerance limits for timing).

Appendix 2 lists the clinical laboratory tests that will be performed for this study.

Appendix 4 provides a summary of the maximum number and volume of invasive samples, for all sampling, during the study.

Unless otherwise stated in subsections below, all samples collected for specified laboratory tests will be destroyed within 60 days of receipt of confirmed test results. Certain samples may be retained for a longer period, if necessary, to comply with applicable laws, regulations, or laboratory certification standards.

Investigators must document their review of each laboratory safety report.

## 9.1. Efficacy Assessments

This section is not applicable for this study.

#### 9.2. Adverse Events

Investigators are responsible for monitoring the safety of subjects who have entered this study and for alerting Lilly or its designee to any event that seems unusual, even if this event may be considered an unanticipated benefit to the subject.

The investigator is responsible for the appropriate medical care of subjects during the study.

The investigator remains responsible for following, through an appropriate health care option, AEs that are serious or otherwise medically important, considered related to the investigational product or the study, or that caused the subject to discontinue the investigational product before completing the study. The subject should be followed until the event resolves, stabilizes with appropriate diagnostic evaluation, or is reasonably explained. The frequency of follow-up evaluations of the AE is left to the discretion of the investigator.

After the informed consent form (ICF) is signed, study site personnel will record, via eCRF, the occurrence and nature of each subject's preexisting conditions, including clinically significant signs and symptoms of the disease under treatment in the study. Additionally, site personnel will record any change in the condition(s) and the occurrence and nature of any AEs.

Any clinically significant findings from ECGs, labs, vital sign measurements, and other procedures should be reported as an AE to Lilly or its designee.

The investigator will interpret and document whether or not an AE has a reasonable possibility of being related to study treatment or a study procedure, taking into account the concomitant treatment or pathologies.

A "reasonable possibility" means that there is a cause and effect relationship between the investigational product, study device, and/or study procedure and the AE.

Planned surgeries should not be reported as AEs unless the underlying medical condition has worsened during the course of the study.

If a subject's investigational product is discontinued as a result of an AE, study site personnel must report this to Lilly or its designee via eCRF.

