#### 9.2.1.1. Suspected Unexpected Serious Adverse Reactions

Suspected unexpected serious adverse reactions (SUSARs) are serious events that are not listed in the IB and that the investigator identifies as related to investigational product or procedure. United States 21 Code of Federal Regulations 312.32 and European Union Clinical Trial Directive 2001/20/EC and the associated detailed guidances or national regulatory

requirements in participating countries require the reporting of SUSARs. Lilly has procedures that will be followed for the recording and expedited reporting of SUSARs that are consistent with global regulations and the associated detailed guidances.

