## 10.3.1. Safety Analyses

## 10.3.1.1. Clinical Evaluation of Safety

All investigational product and protocol procedure AEs will be listed and, if the frequency of events allows, safety data will be summarized using descriptive methodology.

The incidence of symptoms for each treatment will be presented by severity and by association with investigational product as perceived by the investigator. Symptoms reported to occur prior to enrollment will be distinguished from those reported as new or increased in severity during the study. Each symptom will be classified by the most suitable term from the medical regulatory dictionary.

The number of investigational product-related SAEs will be reported.

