9.4 Safety and Tolerability Assessments

9.4.1 Adverse events

Where changes in severity are recorded in the Case Report Form (CRF), each separate severity of the AE will be reported in the listings, only the most severe will be used in the summary tables. A pre-existing condition is defined as an AE that starts before the subject has provided written informed consent and is ongoing at consent. A non-treatment emergent AE is defined as an AE which starts after informed consent but prior to dosing. A treatment-emergent AE is defined as an AE which occurs postdose or which is present prior to dosing and becomes more severe postdose.

All AEs will be listed. Treatment-emergent AEs will be summarized by severity and relationship to the study drug. The frequency (the number of AEs, the number of subjects experiencing an AE and the percentage of subjects experiencing an AE) of treatment-emergent AEs will be summarized by Medical Dictionary for Regulatory Activities (MedDRA) version 20.1 system organ class and preferred term. The summary and frequency AE tables will be presented for all causalities and those considered related to the study drug. Any serious AEs will be tabulated. Onset time of AEs will derived relative to the oral administration.

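### Protocol 9.2 defines a reasonable possibility of relatedness as an existing causal relationship, contradicting the question put to the investigator and risking under-classified or inconsistent relatedness coding

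*Protocol*

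**What the plan says.** The operative instruction in Protocol 9.2 is: "The investigator will interpret and document whether or not an AE has a reasonable possibility of being related to study treatment or a study procedure". The judgement is to take account of other treatments and conditions. The next sentence defines the key term: a reasonable possibility "means that there is a cause and effect relationship between the investigational product, study device, and/or study procedure and the AE".

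Neither Protocol Appendix 1 nor SAP 9.4.1 gives another definition of relatedness. Several later provisions use the investigator's call:

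- SAP 9.4.1: "The summary and frequency AE tables will be presented for all causalities and those considered related to the study drug".
- Protocol 10.3.1.1: "The number of investigational product-related SAEs will be reported".
- Protocol 9.2.1.1: SUSARs "are serious events that are not listed in the IB and that the investigator identifies as related to investigational product or procedure".
- Protocol 9.2.1: an SAE learned of after the subject has left the study must be notified if the investigator thinks it reasonably possibly related.

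Other provisions do not use it. SAP 9.4.1 also states: "All AEs will be listed", and "Any serious AEs will be tabulated". Protocol 9.2.1 requires the site to alert the sponsor to any SAE within 24 hours, and after dosing this carries no causality condition.

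**The concern.** The definition contradicts the term it defines. The question asks for a suspicion; the definition asks for a relationship that exists. An investigator who follows the second sentence could code a plausible but unproven event as not related. One who follows the first would code the same event as related.

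The stricter standard is also hard to meet in this design. There is a single period and one dosing day, with no comparator, and oral and intravenous drug are given together. Causation of an individual event can be suspected but hardly established.

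Safety is a secondary objective, and Protocol 7.4.1.2 describes this as the first intravenous administration of the labelled compound. Any error from a literal reading runs towards too few attributed events.

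**Working it through.** No formula or planned figure is at issue, so the check sets the passages side by side.

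**Step 1: the standards.**

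| Place | Standard |
|---|---|
| Protocol 9.2, question | Reasonable possibility |
| Protocol 9.2, definition | Cause and effect relationship exists |
| Protocol 9.2.1 | Reasonably possibly related |
| Protocol 9.2.1.1 | Suspected reaction, identified as related by the investigator |
| Protocol 9.4.6 | Suspected drug-induced rash |

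The definition is the outlier. Under it, a rash could trigger the suspected-rash procedure in 9.4.6 and still be coded not related.

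**Step 2: what depends on the call, and what protects it.**

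| Output or action | Depends on relatedness? | What remains under a literal reading |
|---|---|---|
| Related-only AE tables (SAP 9.4.1) | Yes | All-causality versions of the same tables; full AE listing |
| Product-related SAE count (Protocol 10.3.1.1) | Yes | Tabulation of every SAE (SAP 9.4.1) |
| SUSAR identification (Protocol 9.2.1.1) | Yes, by the investigator's call | 24-hour notice of any on-study SAE after dosing (9.2.1); sponsor review of SAEs (9.4.6); sponsor procedures said to follow global regulations (9.2.1.1) |
| SAE between consent and dosing (Protocol 9.2.1) | Yes, for SAE reporting | Still recorded as an AE in the case report form |
| SAE learned of after the study (Protocol 9.2.1) | Yes | No all-SAE requirement found |
| AE follow-up duty (Protocol 9.2) | In part | Serious or medically important AEs, and those causing discontinuation of product, are followed anyway |
| AE listing, all-causality tables, SAE tabulation | No | Unchanged |
| Primary bioavailability analysis | No | Unchanged |

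The post-study route is the most exposed. It is conditional on relatedness, and no other provision captures the event. Section 9.2.1 uses slightly different words from 9.2, so an investigator may or may not carry the definition across.

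**Step 3: scale.** SAP 8 defines the Safety population as all enrolled subjects, and up to 8 may be enrolled. If n = 8, a subject whose only related event is recoded moves a related-AE percentage by 1/n = 1/8 = 12.5 points. The all-causality percentage does not move.

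**The case against.** The strongest reply is that investigators will read the sentence sensibly. The instruction still asks "whether or not an AE has a reasonable possibility of being related to study treatment or a study procedure" and calls for judgement. Protocol 10.3.1.1 reports association as the investigator perceives it, and SAP 9.4.1 speaks of events considered related. The case report form instructions and SAE forms are not in the documents, so actual coding cannot be known. This stands as a limit on the consequence: nothing shows that investigators would demand established causation. It does not rescue the sentence. Perception says who judges, not by what standard, and a definition that works only when ignored should be corrected. If some investigators ignore it and others do not, coding is inconsistent.

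The second reply is that the safeguards are substantial. That also stands, for everything in the second table except the post-study route. The SUSAR safeguards are partial: the sponsor receives every on-study SAE after dosing, but Protocol 9.2.1.1 still makes the investigator's call part of the definition.

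A reader might go further and infer that every plausible but unproven event will be scored not related, so that the related count falls towards zero. The documents do not support that. It assumes uniform literal use, and even a strict investigator may be satisfied on clinical grounds that a product or procedure caused an event.

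A reader might also look for a size in the 1% to 10% event frequencies in Protocol 3.2.1.2. With 8 subjects, the chance that at least one has a given event is 1 − 0.99^8 = 0.077 at 1% and 1 − 0.90^8 = 0.570 at 10%. Those are chances that an event occurs, not that it is suspected and then miscoded, and the frequencies are not split by relatedness.

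**Conclusion.** The point holds as a defect of wording with a possible, unquantified effect on safety coding. The sentence is wrong as written because it conflicts with its own question and with the standards in Protocol 9.2.1, 9.2.1.1 and 9.4.6. The effect on the related-only outputs, SUSAR identification and post-study notification is conditional on at least some investigators applying the definition literally. No magnitude is claimed beyond the 1/n step, which would apply to any recoded subject. No event is lost from the AE listing, and no inferential safety analysis is planned (SAP 9.4.8).

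**What to change.** Reword the defining sentence in Protocol 9.2 so that a reasonable possibility means there may be a causal relationship. For example: *A reasonable possibility means that a causal link between the event and the product, device or procedure is plausible; the link need not be established.* This matches Protocol 9.2.1 and 9.2.1.1, so the tables, the SAE count and both reporting routes would rest on one standard.

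SAP 9.4.1 needs no separate rule. The cost is one protocol sentence, with no extra data or subjects. The small downside is that some more events may be classed as related.
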